4.4 Quantitative Data Analysis

The ATLAS codebook ([Appendix B](#)) includes codes to facilitate quantitative summarization (descriptive analysis) of interview participants' reports related to DPNP symptoms and impacts. In the analysis and reporting of frequencies or counts of these concepts, only unique mentions per code per patient will be counted.

- Frequency and percentage of interview participants reporting each DPNP symptom/sensation before the clinical trial
- Frequency and percentage of interview participants reporting pain in specific locations (e.g., hands, arms, feet)
- Frequency and percentage of interview participants reporting a specific location (e.g., hands, arms, feet) as the location where their pain is most severe
- Frequency and percentage of interview participants reporting a specific location (e.g., hands, arms, feet) as the most bothersome
- Frequency and percentage with which each symptom or sensation was reported as the most bothersome
- Frequency and percentage of DPNP impacts reported before the clinical trial
- Frequency and percentage of a DPNP symptom being reported as the most important to treat prior to starting the clinical trial

Descriptive statistics (frequencies, mean, range) will be computed for the following assessments for the overall interview sample and by treatment assignment, as provided by Lexicon (LX9211 treatment [10 mg or 20 mg] or placebo):

- Clinical and demographic characteristics reported (e.g., sex, age, age of diagnosis of diabetes, age at onset of DPNP symptoms)
- Frequency and percentage of interview participants reporting specific symptom improvements during the clinical trial
- Frequency and percentage of improvement in a symptom (reported during the clinical trial) being reported as the most important improvement
- Frequency and percentage of specific impacts of symptom improvements being reported across interview participants

- Satisfaction with treatment before and after the clinical trial
 - 0 = not at all satisfied, 1 = a little satisfied, 2 = moderately satisfied, 3 = quite satisfied, and 4 = very satisfied
- Difficulty managing DPNP before the clinical trial
 - 0 = not at all difficult, 1 = a little difficult, 2 = moderately difficult, 3 = quite difficult, 4 = very difficult
- Ratings for how important it would be for a treatment to improve specific symptoms
 - 1 = not at all important, 2 = a little important, 3 = moderately important, 4 = very important, 5 = extremely important

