 2 = Moderately difficult
 3 = Quite difficult
 4 = Very difficult

- Tell me why you selected that answer.

III. Prestudy Impact/Burden Of DPNP	~ 10 min
--	-----------------

10. **Before starting the study, what impact did diabetic neuropathic pain have on your life, if at all? [Allow for spontaneous reports of impacts. Specific probes are listed below]**

11. **How, if at all, did this pain affect your life before the study? [Probe for impact areas if not spontaneously reported]...**

- a) Daily activities? What kinds of daily activities were impacted?
 - Are there things you could not do because of the pain that you wanted to do?
- b) Mobility (e.g., walking; using stairs; getting up/down from chair or toilet)
- c) Mood/emotions (e.g., depressed mood, anxiety, irritability, anger)
- d) Self-care (e.g., bathing or dressing self; using utensils)
- e) Sleep

12. **What was it about your neuropathic pain or its treatment that bothered you the most before starting the study? [Probe to understand if most bothersome issues are issues related to the pain and/or are treatment-related]**

Why does [repeat most bothersome issue] bother you?

IV. Prestudy Treatment Expectations

~ 5 min

13. Thinking back to before you started the clinical trial, what were some of the reasons you decided to participate in the trial?
 - a) Were some reasons more important to you than others? **[If yes]** Which ones?
14. Before starting the clinical trial, were there specific symptoms/problems that you most wanted the study drug to help? Which ones? Why?
15. How important to you would it be for a neuropathic pain treatment to improve? **[Use the 1-to-5 rating scale below for each symptom the patient reports – examples listed below. Repeat scale as often as needed]**
 - 1 = Not at all important
 - 2 = A little important
 - 3 = Somewhat important
 - 4 = Very important
 - 5 = Extremely important
 - a) Pain
 - b) Numbness
 - c) Tingling/pins and needles
 - d) Weakness

V. During Study Experiences

~ 15 min

Now I would like to talk to you about your experiences during the clinical study. So, thinking about your experiences while you were taking the study drug....

- 16. What were your overall impressions of the study drug?**

- 17. What improvements, if any, did you notice while taking the study drug?**

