[Ask the participant to describe each improvement reported. Allow for spontaneous reports of improvements in symptoms/pain. If not already mentioned, probe to see if the symptoms experienced before the study improved, if so, have the participant describe the improvement and rate the importance of the improvement below]

- 18. Please rate the importance of the improvement in [SYMPTOM from Q4] on the following scale (from 1 to 5). I will read the scale to you:**

 1 = Not at all important
 2 = A little important
 3 = Moderately important
 4 = Very important
 5 = Extremely important

Why?

[If improvements noticed] How soon after receiving the study drug did you notice these improvements?

- a) What, specifically, did you notice first?

VI. Impact of Improvements [If no improvements, skip to Q 23] ~ 10 min

19. Thinking about the improvements [Refer back to improvements listed above] you noticed as a result of the study drug, which are the most important to you? Why?
20. Thinking about the improvements you have seen from the study drug; how did these improvements affect you in your daily life? [Allow for spontaneous responses]

[If not reported spontaneously] How, if at all, did these improvements affect your...

- a) Daily activities? What kinds of daily activities were impacted?
 - Are there things you can now do or do better because of improvements in neuropathic pain?
- b) Mobility (e.g., walking; using stairs; getting up/down from chair or toilet)
- c) Mood/emotions (e.g., depressed mood, anxiety)
- d) Self-care (e.g., bathing or dressing self; using utensils)
- e) Sleep

21. You mentioned that that [insert response from Q14] bothered you the most. How, if at all, did the study drug improve these issues?

VII. Treatment Satisfaction and Preference

~ 5 min

22. Overall, how satisfied are you with the study drug as a treatment for diabetic neuropathic pain?

- 0 = Not at all satisfied
- 1 = A little satisfied
- 2 = Moderately satisfied
- 3 = Quite satisfied
- 4 = Very satisfied

- a) Tell me why you selected that response. [Probe to better understand what specifically influenced participant's response to this question]

23. Thinking about the study drug compared to the neuropathic pain treatment(s) you had tried before the study, which did you prefer:

- Study drug
- A previous medication

Why?

24. Would you have continued taking the study drug if you could have?

- Yes
- No

Why?

VIII. Summing Up

~ 2 min

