6.6	Sx_Treat_Importance_Sensitivity	Response to question "How important would it be to you for a neuropathic pain treatment to improve sensitivity?"
6.7	Sx_Treat_Importance_Other	Response to question "How important would it be to you for a neuropathic pain treatment to improve [any other symptom patient reported]?"
7.0 Study Experiences		Code any symptom improvement mentioned (no matter how slight) and description of improvement.
7.1	Overall impressions of the study drug	Code response to question "What were your overall impressions of the study drug?"
7.2	Improve_Numbness	Neuropathic pain described as numbness or dead feeling
7.3	Improve_Tingling	Neuropathic pain described as tingling or pins and needles
7.4	Improve_Weakness	Neuropathic pain described as weakness
7.5	Improve_Sensitivity	Neuropathic pain described as very sensitive or sensitivity to touch and pressure
7.6	Improve_Other	Any other descriptions of neuropathic pain
7.12	No_Improvement	If the study participants reported no improvements in symptoms during the clinical trial
7.13	Noticed improvements	Code response to question "How soon after receiving the study drug did you notice these improvements" and all related probes

Code		Operational Definition
8.0 Importance of Symptom Improvement		These codes are participant's responses to importance rating of each symptom improvement from interview guide. Code entire response.
8.1	Why_Important	Code entire importance rating, why
8.2	Most Important Improvement	Response to the following question: "Thinking about the improvements you noticed as a result of study drug, which are the most important? Why?"
9.0 Impact of Improvement		Code any reports of improvements/reductions in the impact of their DPNP due to improvements in symptoms during study treatment
9.1	Tx_Impact_daily activities_work	Impact on any gainful activities (e.g., absenteeism, productivity)
9.2	Tx_Impact_daily activities_home	Impact on activities completed at home (running a household, caring for family)
9.3	Tx_Impact_mobility	Impact on walking, using stairs, getting up/down from a chair or toilet, etc.
9.4	Tx_Impact_mood/emotions	Impact on mood/emotions/feelings, such as depressed mood, anxiety, irritability, anger
9.5	Tx_Impact_self-care	Impact on ability to engage in self-care activities such as bathing, dressing, using utensils
9.6	Tx_Impact_sleep	Impact on ability to get to sleep or stay asleep

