Treatment Group	0 (Not at all satisfied) n (%)	1 (A little satisfied) n (%)	2 (Moderately satisfied) n (%)	3 (Quite satisfied) n (%)	4 (Very satisfied) n (%)
Overall					
n (%)					
Mean, Median (SD)					
Min-Max					
LX9211 All					
n (%)					
Mean, Median (SD)					
Min-Max					
LX9211 10 mg					
n (%)					
Mean, Median (SD)					
Min-Max					
LX9211 20 mg					
n (%)					
Mean, Median (SD)					
Min-Max					
Placebo					
n (%)					
Mean, Median (SD)					
Min-Max					

ADPS = average daily pain score; DPNP = diabetic peripheral neuropathic pain; SD = standard deviation.

Correlation between Satisfaction with previous DPNP treatment and baseline ADPS: $r = 0.xx$; $n = xx$

Table C-15. Study Drug Treatment Satisfaction at End of Treatment by Treatment Group

Treatment Group	0 (Not at all satisfied) n (%)	1 (A little satisfied) n (%)	2 (Moderately satisfied) n (%)	3 (Quite satisfied) n (%)	4 (Very satisfied) n (%)
Overall					
LX9211 All					
LX9211					
10 mg					
LX9211					
20 mg					
Placebo					

Table C-16. Change from Baseline in ADPS by Study Drug Treatment Satisfaction at End of Treatment

Treatment Group	0 (Not at all satisfied) n (%)	1 (A little satisfied) n (%)	2 (Moderately satisfied) n (%)	3 (Quite satisfied) n (%)	4 (Very satisfied) n (%)
Overall					
n (%)					
Mean, Median (SD)					
Min-Max					
LX9211 10 mg					
n (%)					
Mean, Median (SD)					
Min-Max					
LX9211 20 mg					
n (%)					
Mean, Median (SD)					
Min-Max					
Placebo					
n (%)					
Mean, Median (SD)					
Min-Max					

ADPS = average daily pain score; SD = standard deviation.

Correlation between Satisfaction with study drug and change from baseline ADPS: $r = 0.xx$; $n = xx$

Table C-17. Treatment Preference by Treatment Group

Preference	LX9211 10 mg, n (%)	LX9211 20 mg, n (%)	LX9211 All, n (%)	Placebo, n (%)	Total, n (%)
Study drug					
Previous DPNP medication					

DPNP = diabetic peripheral neuropathic pain.

Table C-18. Change from Baseline in ADPS and Treatment Preference

Preference	Study Drug	Previous DPNP Medication
Overall		
n (%)		
Mean, Median (SD)		
Min-Max		
LX9211 All		
n (%)		
Mean, Median (SD)		
Min-Max		
LX9211 10 mg		
n (%)		
Mean, Median (SD)		
Min-Max		
LX9211 20 mg		
n (%)		
Mean, Median (SD)		
Min-Max		
Placebo		
n (%)		
Mean, Median (SD)		
Min-Max		

ADPS = average daily pain score; SD = standard deviation.

Table C-19. Desire to Continue Study Drug by Treatment Group

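### The interview guide routes patients who report no improvement past the study-drug satisfaction question, although the plan analyses that rating in the whole interview sample and by arm

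*SAP*

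**What the plan says.** All of this is in the qualitative interview plan bound with the SAP.

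- **Who counts as not improved.** Appendix A, Question 17: "What improvements, if any, did you notice while taking the study drug". The answer is the patient's own report, after probing for each pre-study symptom. Appendix B has a code for patients with none: "If the study participants reported no improvements in symptoms during the clinical trial".
- **The skip.** Appendix A, heading of Section VI: "VI. Impact of Improvements [If no improvements, skip to Q 23". Section VI holds Questions 19 to 21.
- **The question passed over.** It is the first item of Section VII, rated 0 to 4: "22. Overall, how satisfied are you with the study drug as a treatment for diabetic neuropathic pain".
- **Where the skip lands.** "23. Thinking about the study drug compared to the neuropathic pain treatment(s) you had tried before the study, which did you prefer".
- **What is to be analysed.** Section 4.4 says that descriptive statistics "will be computed for the following assessments for the overall interview sample and by treatment assignment", and its list includes satisfaction before and after the trial. Table C-15 gives end-of-treatment satisfaction by arm. Table C-16 is titled "Change from Baseline in ADPS by Study Drug Treatment Satisfaction at End of Treatment" and has a correlation with its n beneath it. Neither table is limited to patients who improved, and neither has a row or column for patients who were not asked.

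**The concern.** Question 22 does not presuppose any improvement, since its scale starts at not at all satisfied. The patients passed over are those most likely to use the low end of that scale. They are also the likeliest source of reasons for dissatisfaction, which Section 1 of the plan lists among the interview objectives and which the follow-up probe to Question 22 is meant to collect.

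Whether a patient reports improvement is itself an outcome of treatment. Limiting the rating to those who do makes the arm comparison one between groups selected after randomisation. The pre-trial rating (Question 8) is asked of everyone, so the before and after figures would describe different sets of patients. A reader of Tables C-15 and C-16 would have no sign of this.

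**Working it through.** The plan states no figure to reproduce. The main check traces the guide against the analysis plan. The numbers after it are illustrations.

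**1. Route of a patient with no improvement.** Question 17 (none reported), then the Section VI heading, then Question 23. Questions 19, 20, 21 and 22 are not asked. Questions 23 (preference) and 24 (wish to continue) are.

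**2. Is the rating collected elsewhere?** No. Question 8 is satisfaction with treatment before the trial. Question 16 asks for open-ended impressions. Codebook item 10.1, the only code for study-drug satisfaction, is defined by the wording of Question 22.

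**3. Do the analyses allow for the gap?** No. Section 4.4, Table C-15, Table C-16 and the correlation refer to the interview sample and the arms without restriction.

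**4. Is it a numbering slip?** Probably. The question on how soon improvements were noticed, just before Section VI, has a sub-item but no number. If it were Question 19, each later question would move up by one and satisfaction would be Question 23, the skip target. Question 21 also takes the most bothersome problem from Question 14, whereas Question 12 asks for it.

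**5. How many would be asked.** The number asked is N × (1 − share reporting no improvement). N is up to 60 in Section 1 of the qualitative plan, and 60 to 85 in Protocol Section 6 and SAP Section 2.2. The documents give no share, so 20% to 50% is assumed.

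- N = 60: 60 × 0.8 = 48, down to 60 × 0.5 = 30.
- N = 85: 85 × 0.8 = 68, down to 85 × 0.5 = 42.5.

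**6. Direction of the arm contrast.** For each arm, the mean in all patients is p × (score in improved) + (1 − p) × (score in others), where p is the share reporting improvement. As printed, only the score in improved patients is seen. All inputs are assumed, with a score of 1 for patients without improvement.

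| Assumed p and score in improved | Mean, all: active | Mean, all: placebo | Difference, all | Difference as printed |
|---|---|---|---|---|
| p 0.6 / 0.4; score 3 / 3 | 0.6×3 + 0.4×1 = 2.2 | 0.4×3 + 0.6×1 = 1.8 | 0.4 | 3 − 3 = 0 |
| p 0.6 / 0.4; score 3.5 / 2.5 | 0.6×3.5 + 0.4×1 = 2.5 | 0.4×2.5 + 0.6×1 = 1.6 | 0.9 | 3.5 − 2.5 = 1.0 |
| p 0.5 / 0.5; score 3.5 / 2.5 | 0.5×3.5 + 0.5×1 = 2.25 | 0.5×2.5 + 0.5×1 = 1.75 | 0.5 | 3.5 − 2.5 = 1.0 |

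The difference can shrink or grow. The mean in each arm rises in every row.

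**7. A less schematic illustration.** A simulation took the 1-unit difference and SD of 2 from Protocol Section 10.1. It assumed a mean pain reduction of 0.5 to 1.5 on placebo, satisfaction that rises with pain reduction, and lower satisfaction in patients reporting no improvement. Restricting to patients who report improvement had these effects:

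- mean placebo satisfaction rose from about 1.5–2.1 to 2.3–2.7;
- the arm difference fell from about 0.44–0.50 to 0.20–0.32;
- the correlation with pain reduction fell from about 0.62–0.70 to 0.46–0.55.

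These sizes, and the fall in the arm difference, belong to the assumptions. Step 6 shows that other assumptions reverse the latter.

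**The case against.** The strongest reply is that this is a stale cross-reference in a semistructured interview, and that an experienced interviewer would ask Question 22 anyway. The first half is probably right, and it makes the point an internal contradiction rather than a deliberate choice. It does not remove it: the guide is titled final, the skip is explicit, and nothing in the plan tells the interviewer to override it.

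A second reply is that few patients may be skipped. Question 17 is followed by symptom-by-symptom probing, and the codebook counts any improvement, however small. That stands. The 20% to 50% range is an assumption, and the true share could be lower.

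A third is that little depends on the result. That also stands. The substudy is optional, thematic and descriptive, and is reported separately. No primary, secondary or safety analysis uses it. Preference and wish to continue are asked of everyone, so Tables C-17 to C-20 are unaffected.

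A reader might go further and infer that the skip shrinks the arm difference, or hides it altogether. The documents do not support this. The case that gives zero gets there only because it assigns the same score to improved patients in both arms, and other plausible scores make the difference grow. That more placebo patients would be skipped also presumes that the drug works.

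**Conclusion.** The point holds as a contradiction between the printed guide and the planned analysis. It follows from the text alone and needs no assumption. As printed, study-drug satisfaction is observed only in patients who say at Question 17 that they improved. This group should not be read as ADPS responders, because no diary threshold is involved.

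Mean satisfaction is likely inflated, on the modest assumption that patients who notice no improvement are less satisfied on average. The before/after comparison uses different patients, and the correlation in Table C-16 is computed in a selected group. The arm contrast is open to bias whose direction and size the documents do not determine. The defect should be corrected, but it reaches no further than the satisfaction results of this substudy.

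**What to change.** Change the Section VI instruction so that patients with no improvement go to Question 22. Questions 19 to 21 still do not apply to them. The cost is one number in the guide, plus one rating and its follow-up probe for each such patient. The Question 14 reference inside Question 21 should be checked in the same pass.

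The qualitative plan is dated 02 April 2020 and the SAP 07 June 2022, so some interviews may already have followed the printed skip. For those, the missing ratings cannot be recovered by editing the guide. Label Table C-15, Table C-16 and the correlation as restricted to patients reporting improvement, show the number not asked in each arm, and limit any before/after comparison to patients with both ratings. This costs a footnote and one added row per table.

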Additionally, the clinical study sponsor will share limited data from the clinical study with us so that we can better understand experiences of participants in the study. For example, they may share with us scores from some of the questionnaires you completed as part of the clinical study and your responses to certain questions about how well the drug worked for you.

Do you have any questions before we begin? [\[Answer any questions.\]](#)

START RECORDING

[Once the recording starts, the interviewer will verbally record the participant's clinical study ID and interview date for the audio]

We have started the audio recording. Do we have your permission to continue with the interview?

Yes → [CONTINUE](#)
 No → [STOP INTERVIEW](#)

II. Background Information and Prestudy Experiences **~ 10 min**

[RECORD]

First, I would like to learn a little more about you and about your experiences with diabetic neuropathic pain

1. **How old are you? _____ years** [\[Confirm from recruitment grid\]](#)
2. **About how old were you when you were diagnosed with diabetes?**
_____ (years old)
3. **About how long ago did you start to experience neuropathic pain associated with your diabetes?** _____ (months/years)

4. Before starting the study, in your own words, what did this pain feel like?

[If not reported spontaneously probe for the presence of the following]

- a) Numbness/dead feeling**
- b) Tingling/pins and needles**
- c) Weakness**
- d) Very sensitive/heightened sensitivity to touch and pressure**

5. Before starting the study, where did you experience your neuropathic pain?

- a) Hands**
- b) Arms**
- c) Feet**
- d) Legs**
- e) Other** _____

6. [If experienced in more than 1 location] Were there specific locations where the pain was more severe than others before starting the clinical trial? [If yes] Which ones?

7. [If more than one symptom experienced] Were specific symptoms more bothersome to you than others before starting the clinical trial? [If necessary, remind patient of the symptoms reported in Q4]. [If yes] Which ones?

8. Before starting the clinical trial, overall, how satisfied were you with your neuropathic pain treatment(s)?

- 0 = Not at all satisfied
- 1 = A little satisfied
- 2 = Moderately satisfied
- 3 = Quite satisfied
- 4 = Very satisfied

- Tell me why you selected that answer.

9. **Before starting the clinical trial, how easy or hard was it for you to manage your neuropathic pain?**

0 = Not at all difficult
 1 = A little difficult

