4.2 Pre-trial pain management	Responses to the questions "Before starting the clinical trial, how easy or hard was it for you to manage your neuropathic pain?" and "Tell me why you selected that answer."
5.0 DPNP Impacts Before Clinical Trial	Code response to the question "Before starting the study, what impact did diabetic neuropathic pain have your life, if at all" and follow-up probes.
5.1 Impact_daily_activities_work	Impact on any gainful activities (e.g., absenteeism, productivity)
5.2 Impact_daily_activities_home	Impact on activities completed at home (running a household, caring for family)
5.3 Impact_mobility	Impact on walking, using stairs, getting up/down from a chair or toilet, etc.
5.4 Impact_mood/emotions	Impact on mood/emotions/feelings, such as depressed mood, anxiety, irritability, anger
5.5 Impact_self-care	Impact on ability to engage in self-care activities such as bathing, dressing, using utensils
5.6 Impact_sleep	Impact on ability to get to sleep or stay asleep
5.7 No_impact	Patient reports no impacts
5.8 Most bothersome problem - DPNP_Symptom	Response to the question "What was it about your neuropathic pain or treatment that bothered you the most before starting the study?" for all symptom responses and related probes
5.8 Most bothersome problem - DPNP_Treatment	Response to the question "What was it about your neuropathic pain or treatment that bothered you the most before starting the study?" for all treatment responses and related probes

Code		Operational Definition
6.0 Clinical Trial Desires/Expectations		Code responses to questions related to prestudy treatment expectations
6.1	Reasons_CT	Response to question "Thinking back to before you started the clinical trial, what were some of the reasons you decided to participate in the trial?" and "Were some reasons more important to you than others? Which ones?"
6.2	Sx_Treat_CT	Response to question "Before starting the clinical trial, were there specific symptoms that you most wanted the study drug to help? Which ones? Why?"
6.3	Sx_Treat_Importance_Numbness	Response to question "How important would it be to you for a neuropathic pain treatment to improve numbness?"
6.4	Sx_Treat_Importance_Tingling	Response to question "How important would it be to you for a neuropathic pain treatment to improve tingling?"
6.5	Sx_Treat_Importance_Weakness	Response to question "How important would it be to you for a neuropathic pain treatment to improve weakness?"

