9.7	Tx_Impact_most bothersome	Treatment improvement (if any) on symptom or impact reported as most bothersome

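### Question 21 of the exit-interview guide reads back the answer to Question 14 as what bothered the patient most, which Question 14 does not ask

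*SAP*

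**What the plan says.** The interview guide is Appendix A of the qualitative analysis plan that follows the main SAP, and it is labelled final. Four of its questions matter here.

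- Question 7 (Section II): "Were specific symptoms more bothersome to you than others before starting the clinical trial".
- Question 12 (Section III): "What was it about your neuropathic pain or its treatment that bothered you the most before starting the study". The interviewer is told to find out whether the issue lies in the pain, its treatment, or both.
- Question 14 (Section IV): "were there specific symptoms/problems that you most wanted the study drug to help".
- Question 21 (Section VI): "You mentioned that that [insert response from Q14] bothered you the most", followed by "How, if at all, did the study drug improve these issues".

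The codebook (Appendix B) defines code 9.7 as "Treatment improvement (if any) on symptom or impact reported as most bothersome". Section 2.2 of the plan lists, among its research questions, how well the drug treats the symptoms that patients named as most bothersome or as important to treat. Section 5 commits the report to results on every research question in Section 2.

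**The concern.** The two halves of Question 21 point to different earlier answers. The lead-in uses the language of Question 12, but the insert comes from Question 14. An interviewer who follows the guide attributes to the patient a statement that was not the reply to Question 14, and then asks about improvement in that item.

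At stake is one descriptive finding of the interview substudy. The report could say that the drug did, or did not, help with patients' most bothersome problem when a different problem was discussed. The line is read aloud to patients from a finished guide, so a later change to the codebook cannot recover a question that was never put.

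**Working it through.** No arithmetic applies to the inconsistency itself. The check is a comparison of texts.

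1. **Does any question other than 14 supply the wording of Question 21?** Yes. Question 12 is the only question that asks what bothered the patient most. Question 7 asks about relative bother, for symptoms alone. Question 14 does not mention bother.

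2. **Does the plan treat the two ideas as one?** No. Code 5.8 takes the most bothersome problem from "What was it about your neuropathic pain or treatment that bothered you the most before starting the study" and has separate entries for symptom and treatment answers. Code 3.12 holds the Question 7 answer. Code 6.2 holds the Question 14 answer: "were there specific symptoms that you most wanted the study drug to help? Which ones? Why". Sections 2.1 and 4.4 list most bothersome and most wanted treated as separate items, and Tables C-7 and C-8 give each its own shell.

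3. **Can the answers differ?** Yes, by construction. Question 12 admits complaints about earlier treatment, whereas Question 14 asks what the study drug should help.

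4. **Who is exposed?** Section VI is skipped when the patient reports no improvement, so only patients reporting improvement reach Question 21. Among them:
   - If the answers to Questions 12 and 14 agree, the read-back is true in substance and nothing is lost.
   - If they differ and the Question 12 answer is a symptom or an impact, Question 21 addresses another item. Question 17 has already probed whether pre-study symptoms improved, and Question 20 probes activities, mobility, mood, self-care and sleep, so the information may still be in the transcript.
   - If they differ and the Question 12 answer concerns treatment, neither Question 17 nor Question 20 probes it. Question 23 asks which treatment the patient prefers and why, and may reach it by chance.

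5. **How many interviews?** The count is N × (share reporting improvement) × (share of those whose answers differ). For N, Protocol Section 6 and SAP Section 2.2 give 60 to 85, while Section 1 of the qualitative plan gives up to 60. The documents give neither share, so the count could lie anywhere from none to all of those interviewed.

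6. **What output depends on it?** The descriptive list in Section 4.4 does not include improvement in the most bothersome item, and no shell from C-1 to C-20 tabulates code 9.7. Table C-7 describes the period before the trial and does not use Question 21. The dependence runs through the narrative answer to the Section 2.2 research question.

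**The case against.** The strongest reply is that this is one careless line with little downstream effect. The interviews are semistructured, so a patient can correct a false read-back. Code 9.7 is defined by content and quotes no question, so a coder could match the item under code 3.12 or 5.8 to improvements described under Question 17. The codebook is a draft to be revised as coding proceeds. Much of this stands, and it keeps the point small. It does not remove it, because nothing tells interviewers or coders to make the correction.

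Three stronger readings are tempting, and the documents do not support them.

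- A reader might infer that no question covers improvement in the most bothersome problem, so that half of the Section 2.2 question goes unanswered. Questions 17 and 20 cover much of it for symptoms and impacts. What is missing is the direct question and, for treatment-related complaints, any probe at all.
- A reader might apply a guessed rate of disagreement to all 60 to 85 interviews. That counts patients who are never asked Question 21 and rests on a rate found nowhere in the documents.
- A reader might infer that Question 12 was plainly the intended insert. Section 2.2 also covers symptoms important to treat, so Question 14 may have been meant and the lead-in be at fault. Because that research question speaks of symptoms, Question 7 is a candidate too. Question 21 is inconsistent on every one of these readings, but the documents do not say which was meant.

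**Conclusion.** The inconsistency is confirmed on the text alone. For patients who report improvement and whose answers differ, Question 21 asks about something other than what they named as most bothersome, and code 9.7 may then be filled under the wrong description. This assumes that interviewers follow the guide as worded and that coders use the Question 21 reply for code 9.7, which its definition invites but does not require. The effect is confined to a descriptive substudy and leaves the primary, secondary and safety analyses untouched. It is a minor point, worth correcting because the correction is nearly free and the report must address the research question.

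**What to change.** Make the insert and the wording of Question 21 agree. Either insert the Question 12 response (or the Question 7 response if only symptoms are meant), or keep the Question 14 insert and present it as what the patient most wanted treated. Asking both is preferable, since Section 2.2 names both ideas. Divide code 9.7 into improvement in the most bothersome item and improvement in the item most wanted treated.

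For interviews already done, label Question 21 replies as based on Question 14 unless the transcript shows otherwise, and cross-check them against codes 3.12 and 5.8 before reporting anything as most bothersome.

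The guide's other cross-references should be checked at the same time. The skip at the head of Section VI goes to Question 23 and so passes over the satisfaction rating in Question 22.

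The cost is under a minute in an interview planned for about 60 minutes, plus one codebook line.
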